8.2.3 Follow-up of AEs and SAEs

During the course of the study, all AEs and SAEs should be proactively followed up for each patient. Every effort should be made to obtain a resolution for all events, even if the events continue after discontinuation/study completion.

AEs that are unresolved at the patient's last visit in the study must be followed up by the Investigator for as long as medically indicated.

AstraZeneca retains the right to request additional information for any patient with ongoing AE(s)/SAE(s) at the end of the study if judged necessary.

8.2.4 Adverse event data collection

The following variables will be collected for each AE;

- AE (verbatim).
- The date and time when the AE started and stopped.
- CTCAE grade 3 or more: whether the AE is serious or not
- Investigator's causality rating against the Investigational Product (yes or no).
- Action taken with regards to Investigational Product(s).
- Select the appropriate as required: AE caused patient's withdrawal from study (yes or no).
- Outcome.

In addition, the following variables will be collected for SAEs:

- Date AE met criteria for serious AE
- Date Investigator became aware of serious AE
- Reason for AE becoming serious
- Date of hospitalisation
- Date of discharge
- Probable cause of death
- Date of death

- Autopsy performed
- Causality assessment in relation to study procedure(s)
- Causality assessment to other medication/s

8.2.5 Causality collection

The Investigator will assess the causal relationship between Investigational Product and each Adverse Event, and answer 'yes' or 'no' to the question 'Do you consider that there is a reasonable possibility that the event may have been caused by the investigational product?'

For SAEs, a causal relationship will also be assessed for other medication/s and study procedures. Note that for SAEs that could be associated with any study procedure, the causal relationship is implied as 'yes.'

A guide to the interpretation of the causality questions is found in Appendix B to the Clinical Study Protocol.

8.2.6 Adverse events based on signs and symptoms

All AEs spontaneously reported by the patient or care provider or reported in response to open question/s from the study site staff: or revealed by observation will be collected and recorded in the eCRF. When collecting AEs, the recording of diagnoses is preferred (when possible) to recording a list of signs and symptoms. However, if a diagnosis is known, and there are other signs or symptoms that are not generally part of the diagnosis, the diagnosis, and each sign or symptom will be recorded separately.

8.2.7 Adverse events based on examinations and tests

The results from the Clinical Study Protocol-mandated laboratory tests and vital signs will be summarised in the CSR. Deterioration as compared to baseline in protocol-mandated laboratory values, vital signs should, therefore, only be reported as AEs if they fulfil any of the SAE criteria or are the reason for discontinuation of treatment with the investigational product.

If deterioration in a laboratory value/vital sign is associated with clinical signs and symptoms, the sign or symptom will be reported as an AE, and the associated laboratory result/vital sign will be considered as additional information. Wherever possible, the reporting Investigator will use the clinical, rather than the laboratory term (e.g., anaemia versus low haemoglobin value). In the absence of clinical signs or symptoms, clinically relevant deteriorations in non-mandated parameters should be reported as AE(s).

Deterioration of a laboratory value, which is unequivocally due to disease progression, should not be reported as an AE/SAE.

Any new or aggravated clinically relevant abnormal medical finding at a physical examination as compared with the baseline assessment will be reported as an AE unless unequivocally related to the disease under study.

Disease progression can be considered as a worsening of a patient's condition attributable to the disease for which the investigational product is being studied. It may be an increase in the severity of the disease under study and/or increases in the symptoms of the disease. The development of new, or progression of existing metastasis to primary cancer under study should

be considered as disease progression and not an AE. Events, which are unequivocally due to disease progression, should not be reported as an AE during the study.

New cancers

The development of new cancer should be regarded as an SAE. New primary cancers are those that are not the primary reason for the administration of the study drug and have been identified after the patient's inclusion in this study.

Deaths

All deaths that occur during the study, or within the protocol-defined follow-up period after the administration of the last dose of study drug, must be reported as follows:

- Death clearly the result of disease progression should be reported to the study monitor at the next monitoring visit and should be documented in the eCRF but should not be reported as an SAE.
- Where death is not due (or not clearly due) to Progressive Disease (PD) under study, the AE causing the death must be reported to the study monitor as an SAE within 24 hours. The report should contain a comment regarding the co-involvement of PD, if appropriate, and should assign main and contributory causes of death.
- Deaths with an unknown cause should always be reported as an SAE. A post-mortem maybe helpful in the assessment of the cause of death, and if performed, a copy of the post-mortem results should be forwarded to AstraZeneca or its representative within the usual timeframes.

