1. PROTOCOL SUMMARY

1.1 Schedule of Activities (SoA)

Table 1: Schedule of Activities (SoA)

Study Phase	Screening Phase	Treatment Phase ^a		Follow-up Phase
Cycle		Cycles 1-6	EOT	EOS
Visit No.	1	2-7 (Day 1 of each cycle)	8	
Study Days	-6 to 0	1-168 (28 days per cycle)	170	28 days post-EOT
Screening/Enrolment visit				
Informed consent ^s	X			
Eligibility Criteria	X			
Demographics/ Review medical history	X			
ECOG Performance Status	X	X	X	
General Physical examination ^b	X	Symptom-directed physical examination only		
Concomitant medication recording	Continuous from the time of ICF until 28 days after the last Acalabrutinib dose in the treatment phase.			
Study Drug Administration				
Acalabrutinib dosing		The recommended dose is Acalabrutinib 100 mg capsules BID, starting on Day 1 Cycle 1, until disease progression or unacceptable toxicity. Each cycle of treatment is 28 days.		
Disease Evaluations (Disease characteristics will be performed as per routine clinical practice)				
Baseline Disease Characteristics	X			
Safety Evaluations (baseline and each treatment visit) [*]				
Physical examination ^b	X	Symptom-directed physical examination only		
Vital parameters ^c	X	X	X	
Adverse event monitoring	Continuous from the time of ICF until 28 days after last study dose of Acalabrutinib.			

Study Phase	Screening Phase	Treatment Phase ^a		Follow-up Phase
Cycle		Cycles 1-6	EOT	EOS
Visit No.	1	2-7 (Day 1 of each cycle)	8	
Study Days	-6 to 0	1-168 (28 days per cycle)	170	28 days post-EOT
12-lead ECG	X	X	X	
Lymph node biopsy ^d	X			
Next-generation sequencing (NGS)-CLL panel ^e	X			
Haematology ^f & Biochemistry ^g	X	X	X	
Urinalysis ^h	X	X	X	
Pregnancy Test ⁱ	X	X	X	
Chest X-ray ^j	X	X	X	
Efficacy Evaluations (once in 3 months)				
CT/MRI ^k	X	X	X	
EORTC QLQ-C30 Questionnaire	X	X	X	

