[§] Patients must sign the informed consent form before any study-specific procedures are performed. [*] Procedures conducted as part of the patient's routine clinical management (e.g., blood count) and obtained before signing of the Informed Consent Form (ICF) may be utilised for screening or baseline purposes provided the procedures meet the protocol-specified criteria and were performed within the time frame (-6 to 0 day) ^a Treatment phase from Day 1 to Day 168. The treatment with Acalabrutinib will be continued until disease progression or unacceptable drug-related toxicity, whichever occurs earlier. ^b The screening physical examination will include, at a minimum, the general appearance of the subject, height (screening only) and weight, and examination of the skin, eyes, ears, nose, throat, lungs, heart, abdomen, extremities, musculoskeletal system, lymphatic system, and nervous system. Symptom-directed physical examination, including tumour assessments by palpation, are done thereafter. ^c Vital signs (blood pressure, heart rate, and temperature) will be assessed after the patient has rested in the sitting position. ^d Lymph node biopsy will be conducted in patients with lymphadenopathy. However, a report of previous lymph node biopsy performed within 06 months before the study enrolment could be considered if the patient did not receive any medication during that period				

Study Phase	Screening Phase	Treatment Phase ^a		Follow-up Phase
Cycle		Cycles 1-6	EOT	EOS
Visit No.	1	2-7 (Day 1 of each cycle)	8	
Study Days	-6 to 0	1-168 (28 days per cycle)	170	28 days post-EOT

^e Next-generation sequencing will be conducted to understand the genetic profile in Indian settings. Molecular cytogenetics (FISH) for del(13q), del(11q), del(17p), trisomy 12 in peripheral blood lymphocytes; TP53 mutation; immunoglobulin variable heavy chain (IGHV) mutational status will be assessed before the start of treatment in CLL/SLL-naïve patients, or CLL/SLL patients who did not have their report. However, MCL patients are Relapsed/Refractory and their previous report data will be used. A six months old report can be considered for both the conditions.

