^f Haematology will include a complete blood cell count [white blood cell count, haemoglobin (Hb), haematocrit, reticulocyte, and platelet count] and differential leukocyte count, including both percent and an absolute number of lymphocytes. Haematology need not be repeated on Cycle 1 Day 1 if screening haematology was within 5 days

^g Biochemistry will include albumin, Total bilirubin, Total protein, Alkaline Phosphatase (ALP), Alanine Aminotransferase (ALT, SGPT), Aspartate Aminotransferase (AST, SGOT), Gamma-glutamyl transferase (GGT), Lactate Dehydrogenase (LDH), Lipase, Amylase, Blood Glucose, Magnesium, Potassium, Bicarbonate, Sodium, Calcium, Chloride, Creatinine (creatinine clearance), Urea or Blood Urea Nitrogen (BUN), Haptoglobin, b2-microglobulin. Serum biochemistry need not be repeated on Cycle 1 Day 1 if screening chemistry was within 5 days.

^h Urinalysis: pH, ketones, specific gravity, bilirubin, protein, blood, and glucose.

ⁱ A urine pregnancy test will be conducted in all females of child bearing potential at the time of screening and during the study (treatment phase)

^j Chest X-ray will be done as a symptom directed investigation. Patients with signs and symptoms of Pneumonia will be allowed to go for chest X-ray investigation.

^k CT or MRI scans will be performed prior to the first study medication administration (dosing). CT or MRI scans are applicable for the patients with lymphadenopathy or organomegaly. Patients with abnormalities of blood parameters without any lymphadenopathy or organomegaly will not undergo CT or MRI scans. Patients who will be undergoing CT, should have baseline and every 3-months reports

Note: CMV, HIV, and Hepatitis serology testing will be conducted at the screening.

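### Worsening haemoglobin or blood pressure that is asymptomatic, non-serious and does not stop treatment is kept out of the AE data, and the SAP's by-visit statistics cannot show how many patients worsened

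*Protocol*

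**What the plan says.** Protocol 8.2.7 gives its reason first: "The results from the Clinical Study Protocol-mandated laboratory tests and vital signs will be summarised in the CSR". It then says that deterioration from baseline in these parameters "should, therefore, only be reported as AEs if they fulfil any of the SAE criteria or are the reason for discontinuation of treatment". If the change comes with signs or symptoms, the sign or symptom is the AE and the measurement is supporting information. For asymptomatic, clinically relevant deterioration, the section asks for an AE only where the parameter is not mandated. It also excludes changes that are clearly the disease: "Deterioration of a laboratory value, which is unequivocally due to disease progression, should not be reported as an AE/SAE".

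Haemoglobin and blood pressure are both mandated. In the footnotes to the Schedule of Activities, "Haematology will include a complete blood cell count [white blood cell count, haemoglobin (Hb), haematocrit, reticulocyte, and platelet count" is the haematology entry, and "Vital signs (blood pressure, heart rate, and temperature) will be assessed after the patient has rested in the sitting position" covers blood pressure. Both are measured at screening, at the treatment visits and at end of treatment.

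Anaemia and hypertension are named AESIs in protocol section 3 and in the primary endpoint of SAP 6.1.1. SAP 6.3.1 promises frequencies and percentages for AESIs. For laboratory values and vital signs it plans n, mean, median, SD, minimum and maximum of observed values. Mock Tables 14.3.4.1, 14.3.4.2 and 14.3.5 add only a missing count and a row for whether the assessment was done. Mock Table 14.3.1 has no AESI rows. Listings 16.2.15.1, 16.2.15.2 and 16.2.16 hold the values by patient, with a finding column.

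**The concern.** The recording rule rests on the summary: these changes can stay out of the AE log because they will be seen in the laboratory and vital-sign tables. That works only if the tables show worsening. By-visit statistics of observed values describe the group at each visit and do not link a patient's later value to that patient's baseline. Some patients can worsen while others improve and leave the means unchanged.

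The patients affected are those with asymptomatic, non-serious worsening who stay on treatment. If section 8.2.7 is followed, they are not in the AE table, and the planned tables of values do not count them. Safety is the primary objective, two of the named AESIs correspond to mandated measurements, and the interim analysis in SAP 2.5 repeats the primary safety outputs. The plan as written cannot say how many patients had worsening haemoglobin or blood pressure.

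**Working it through.** **1. The plan's own figures.** The only calculation in the plan that bears on this is protocol Table 8, the Clopper-Pearson 95% limits for an incidence. All 43 cells reproduce to two decimals; 20/100, for example, gives 12.67% to 29.18%. No figure in the plan is disputed.

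**2. Can the planned tables yield the count?** Take 100 patients and give baseline and a later visit the same set of 100 normal-shaped values (quantiles at (i - 0.5)/100, scaled to mean 0 and SD 1). Then n, mean, median, SD, minimum and maximum are identical at both visits.
- If each patient keeps the same value, the number falling by at least 1 SD is 0.
- If the k highest baseline values are paired in order with the k lowest later values, the largest k for which every pair differs by at least 1 SD is 61. The continuous bound agrees: 1 - (2Φ(0.5) - 1) = 61.7%.

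The same printed table therefore fits any count from 0 to 61.

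**3. A less extreme version.** Assume bivariate normal values, equal means and SDs, and within-patient correlation ρ. Then P(fall ≥ 1 SD) = Φ(-1/√(2(1 - ρ))). The last column uses the worst of six post-baseline visits (Visits 3 to 8 in the Schedule of Activities) with exchangeable correlation. Its formula is ∫φ(e)[1 - (1 - Φ(e - 1/√(1 - ρ)))⁶]de.

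| Assumed ρ | 1/√(2(1 - ρ)) | One visit, per 100 | Worst of six, per 100 |
|---|---|---|---|
| 0.9 | 2.236 | 1.3 | about 6 |
| 0.7 | 1.291 | 9.8 | about 32 |
| 0.5 | 1.000 | 15.9 | about 45 |
| 0.3 | 0.845 | 19.9 | about 52 |

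The group mean does not move in any row. The 1 SD fall and the correlations are assumptions that show the range; a 1 SD fall is not a definition of anaemia. The last column also limits the remedy: a worst-value count is large even when nothing has changed.

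**4. Effect on an AE-based rate.** The documents give neither the true rate nor the share of cases left out, so both are assumed here. With 20 true cases in 100:
- 25% unrecorded: 15% (8.65 to 23.53)
- 50% unrecorded: 10% (4.90 to 17.62)
- 75% unrecorded: 5% (1.64 to 11.28)

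The last two intervals exclude 20%. Only the direction follows from the documents.

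**5. Precision of an added count.** For an observed 10%: total 10/100 gives 4.90 to 17.62, CLL/SLL 9/90 gives 4.68 to 18.14, and MCL 1/10 gives 0.25 to 44.50. The MCL column can only be descriptive.

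**6. Comparison within the SAP.** Section 6.3.1 plans category counts for ECG and for physical examination. It plans none for laboratory values or vital signs, although the listings carry a finding for both.

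**The case against.** The strongest reply is that section 8.2.7 is a design choice. It avoids recording every out-of-range value twice and prefers the clinical term to the laboratory term. On that reading the AE table counts clinical events and the laboratory tables report measurements. The AESIs have no case definition, so there is no fixed reference against which the count is too low. The listings hold every value, so nothing is lost. This stands in part: the rule is defensible and the counts can be recovered. What it leaves open is that the measurement tables do not show worsening, which is what the rule relies on them for.

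A reader might infer more than the documents support:
- **That no summary is planned.** One is, within the primary endpoint evaluations. It is uninformative about worsening, not absent.
- **That such cases can never reach the AE table.** Section 8.2.6 takes AEs revealed by observation, and recorded AEs feed Table 14.3.1.
- **That sites will record differently.** Section 8.2 and Appendix B 1 are worded more broadly than 8.2.7, but can be read as general text before a specific rule. Divergence is possible, not shown.
- **That AESI rates will not be comparable.** Section 8.2.7 does make an AE of "Any new or aggravated clinically relevant abnormal medical finding at a physical examination", unless unequivocally due to the disease under study, and section 8.1.2 does the same for clinically significant ECG findings. But no planned analysis compares AESI rates with one another.

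A further objection concerns the remedy. A baseline-to-worst count picks up chance variation, and a single-arm study cannot separate that from drug effect. Bounds of only 10 and 11 g/dL, both of which appear in the protocol for other purposes, would never register worsening in a patient enrolled below 10. There is no haemoglobin minimum in the inclusion criteria, and a value below 10 g/dL can itself support eligibility. Both points are right and shape the fix.

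**Conclusion.** The point holds as a gap in the planned summaries. Deterioration in mandated parameters that is asymptomatic, non-serious and does not stop treatment is left out of the AE data, on the strength of a summary that cannot show who worsened. For haemoglobin and blood pressure this touches two named primary AESIs. Any effect on the AE counts is downward, provided 8.2.7 is followed and such cases occur.

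The size of an under-count cannot be derived from the documents, and the illustrations above do not estimate it. What is demonstrated is that the planned statistics leave the number of worsening patients undetermined: 0 to 61 per 100 for a 1 SD fall with identical printed summaries. The documents do not support a claim that the AESI rates will be wrong by a stated amount, or that data are lost. The gap is worth closing because the values are already collected.

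**What to change.** In SAP 6.3.1 and the mock tables, for haemoglobin and blood pressure:
- Define baseline as the last value before the first dose.
- Add change from baseline by visit and a baseline-to-post-baseline shift table.
- Give the number and percentage of FAS patients who worsen by at least one category, with Clopper-Pearson 95% intervals, by cohort and in total. Label the MCL column descriptive.
- Prespecify a full category scale: either one stated CTCAE version where the collected values allow grading (Appendix B 6 and Appendix C cite different versions) or sponsor-stated numeric categories. For haemoglobin, include categories below 10 g/dL, and do not use 10 and 11 g/dL as the only bounds. The documents give no blood-pressure cut-off for this purpose, so the sponsor must state one.
- Show the shift at each scheduled visit as well as to the worst value. State that the worst-value count is all-cause and inflated by chance over repeated visits (about 6 to 52 per 100 with no true change, against 1 to 20 at one visit, under the assumptions above). Flag patients with disease progression.

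In Table 14.3.1, add the AESI rows that 6.3.1 promises and state which MedDRA terms form each row. Show AE-recorded and measurement-based counts side by side, not merged.

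Optionally, reconcile the wording of protocol 8.2, 8.2.7 and Appendix B 1, keeping the exclusion of changes unequivocally due to progression. The protocol planned the last patient's last visit for Q4 2021 and the SAP pages carry an effective date of 25-Nov-2021. On that timetable a changed recording rule would reach few patients, so this part is secondary.

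The cost is SAP text and a few extra tables from values already listed by patient. CTCAE grading may also need local reference ranges, which the haematology listing does not show. The reported figures will look less favourable and will include disease-related and chance changes.

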8.3 Safety reporting and medical management

8.3.1 Reporting of serious adverse events

All SAEs have to be reported, whether or not considered causally related to the investigational product, or to the study procedure(s). All SAEs will be recorded in the eCRF.

If any SAE occurs during the study, the Investigator or other site personnel should inform the appropriate AstraZeneca representatives within one day, i.e., immediately but **no later than 24 hours** of when he or she becomes aware of it.

The Investigator will also inform the chairperson of Institutional Ethics Committee (IEC) and Licensing Authority (LA) i.e., Drugs Controller General (India), about the SAE within **24 hours**. In addition, the Investigator will provide a detailed report on the SAE after due analysis to the IEC chairperson, the Head of Institute and the LA within **14 calendar days** of its occurrence.

The IEC will forward its report on the SAE along with its opinion on the financial compensation, if any, (to be paid by Sponsor) within **30 calendar days** of occurrence of SAE to LA. The timeline for the order from Licensing Authority on the quantum of compensation to be paid will be within **150 calendar days** of occurrence of SAE or receiving report. Sponsor will pay the compensation to subject within **30 calendar days** of order from LA.

In case the Investigator fails to report any SAE within stipulated period, he shall furnish the reason for the delay to the satisfaction of the Licensing Authority along with the SAE report.

The designated AstraZeneca representative will co-ordinate with the Investigator to ensure that all the necessary information is provided to the AstraZeneca Patient Safety data entry site **within 01 calendar day** of the initial receipt for fatal and life-threatening events **and within 05 calendar days** of initial receipt for all other SAEs.

For fatal or life-threatening adverse events where important or relevant information is missing, active follow-up is undertaken immediately. Investigators or other site personnel will inform AstraZeneca representatives of any follow-up information on a previously reported SAE within one calendar day, i.e., immediately but **no later than 24 hours** of when he or she becomes aware of it.

Once the Investigator or other site personnel indicate an AE is serious in the EDC system, an automated email alert is sent to the designated AstraZeneca representative.

If the EDC system is not available, then the Investigator or other study site staff reports an SAE to the appropriate AstraZeneca representative by telephone.

The AstraZeneca representative will advise the Investigator/study site staff on how to proceed.

Investigators or other site personnel will then send relevant eCRF modules by fax to the designated AstraZeneca representative. For further guidance on the definition of an SAE, please refer to Appendix B of the Clinical Study Protocol.

